5.1.2 Secondary Efficacy Endpoints

The secondary efficacy endpoints include the following:

- The incidence of event-free survival (EFS) at 48 weeks, where EFS is defined as high-grade recurrence-free survival (overall population and subgroup of patients with CIS)
- The incidence of EFS at 12, 24, 36, 72, and 96 weeks, where EFS is defined as high-grade recurrence-free survival (overall population and subgroup of patients with CIS)
- Time to recurrence; recurrence is defined as an EFS event
- The incidence of PFS at 48, 72, and 96 weeks as well as time to progression estimated using Kaplan-Meier methods. Progression is defined as the development of T2 or greater disease. Sensitivity analyses will also be performed and will include any of the following as progressions:
 - An increase in stage from Ta or CIS to T1, or
 - Development of T2 or greater, or
 - Lymph node disease, or
 - Distant metastasis
- Overall survival of patients enrolled in the study at 48, 72, and 96 weeks and survival time estimated using Kaplan-Meier methods
- Changes in quality of life over time, as measured by the EORTC QLQ-C30 (a general questionnaire for cancer) and the QLQ-NMIBC24 (a specific questionnaire for NMIBC disease)

This document is confidential.

Additionally, patients with appearance of new high-grade disease (ie, new high-grade papillary disease in patients with CIS only or new CIS in patients with papillary disease only) will be classified as treatment failures in EFS analyses, as will patients with CIS at baseline whose CIS lesions have not resolved by the 12-week cystoscopy, or who have recurrent CIS at later cystoscopies.

At each follow-up visit, response of existing lesions and presence of any new lesions will be evaluated (by direct visualization and biopsies as needed) and reported in the eCRF. Recurrences must be proven and documented by biopsy.

A biopsy will be performed at screening and when indicated by direct visualization at other visits for purposes of staging and grading.

The laboratory results from pathology specimens (samples taken from re-TUR of tumors) will be reviewed by the study investigator. These laboratory results will be provided to the investigator from the certified and/or accredited laboratory local to the site, where the samples were processed. If there is no certified and/or accredited laboratory on site, the specimen may be shipped to another agreed upon certified and/or accredited laboratory for analysis and reporting of results to the study investigator. There is no central laboratory review and/or evaluation requirement in this study. For these efficacy analyses, recurrence will be considered biopsy proven and/or sufficiently documented following a local investigative pathology review that deems the specimen as positive.

In the case where a patient consistently has positive cystoscopy or cytology results (3 or more) but repeated negative biopsy, the patient will **not be** considered a treatment failure for the EFS analyses.

5.2 Safety Endpoints

The safety endpoint is occurrence of treatment-emergent adverse events (TEAEs) according to Common Terminology Criteria for Adverse Events (CTCAE) version 5.0, regardless of relationship to study medication.

This document is confidential.

6. Analysis Populations

The following analysis sets will be evaluated and used for presentation of the data:

Full Analysis Set (FAS)

The FAS will include all patients who are enrolled in the study (ie, signed the ICF) and received at least 1 dose of study medication. This population will be used for efficacy and safety analyses.

Per-Protocol Set

A per-protocol set will include all patients who met all requirements for the target disease at study entry and received all the prescribed treatment without major protocol violations that might have a major effect on efficacy analysis. Classes of major protocol deviations will be defined and documented prior to the conduct of the primary analysis. These will include but are not limited to significant misuse of the drug (eg, wrong dose, missed doses, too long of a delay) and violations of target disease (eg, presence of muscle invasion on subsequent review). These analyses will only be performed if more than 10% of patients are excluded from the per-protocol set (in either CIS or overall population) respectively based on this review. The group of patients excluded will be documented ahead of the protocol snapshot for the evaluation of the primary analysis.

This document is confidential.

7. Statistical Methodology

7.1 Statistical and Analytical Considerations

7.1.1 Statistical Methods

Tabulations will be produced for appropriate demographic, baseline, efficacy, and safety parameters. Continuous variables will be summarized by reporting the number of observations (n), mean, standard deviation (SD), median, minimum, and maximum. Categorical variables will be summarized using frequency tables showing the number and percentage of patients within a particular category, where the denominator is the number of non-missing values within category at applicable time point (unless otherwise specified). Time-to-event data will be summarized using the Kaplan-Meier method.

Table 4: Results Reporting Precision

Statistics	Degree of Precision
Min, Max	The same number of decimal places as recorded in the raw data.
Mean and Median	One more decimal place than the raw data.
SD	Two more decimal place than the raw data.

By-patient data listings will be produced for data collected through the study (e.g., CRF and lab). In general, the data listings will be sorted by site number concatenated with patient number, visit/collection date and visit/collection time (if applicable). All data listings that contain an evaluation date will contain a relative study day (Study Day). Pre-treatment and on-treatment study days are numbered relative to the day of the first dose of study medication, which is designated as Day 1. The preceding day is Day -1, the day before that is Day -2, etc. Baseline will be defined as the last evaluable/non-missing observation/assessment prior to the first dose of study product on Cycle 1, Day 1.

Adverse events will be graded by the Investigator based on the CTCAE, Version 5.0, and will be coded for summarization using the Medical Dictionary for Regulatory Activities (MedDRA® Version 21.0 or later). Concomitant medications will be coded using the World Health Organization (WHO) Drug Dictionary (September 2017 version or later).

7.1.2 Visit Windows

All data will be tabulated per the evaluation visit as recorded on the eCRF, even if the assessment is outside of the visit window.

7.1.3 Handling of Missing Data

Missing data handling rules for AE relationship to treatment and AE severity will be described in Section 7.4.1.

For efficacy endpoints, all efforts will be made to avoid missing data. If, however, it does occur, it will be handled as follows:

- If a visit has been missed and cytology cystoscopy results are available at the next visit and no disease is present, then the earlier visit will be counted as absence of disease.

This document is confidential.

- In addition, the count of absence of disease will be based on visit findings, meaning that if a patient missed a visit and at the next visit he/she experienced a recurrence, the recurrence will be counted only from the day on which evidence was provided.

Patients with CIS lesions that do not resolve by the 12-week cystoscopy will be classified as EFS events. For Kaplan-Meier analyses of EFS, they will be considered to have recurred at 1 day.

Any patient without tumor in the bladder but presence of tumor in the upper urinary tract will not be classified as failures in the CR and EFS analyses and will continue study participation.

Complete dates will be imputed from partial dates of adverse events and medications solely for the purpose of defining treatment emergence for adverse events and prior/concomitant status for medications. The imputed dates will not be presented in the listings. Dates will be defined using the hierarchy of derivations below.

Adverse events:

- For onset date:
 - If only the day part of the AE onset date is missing and occurs in the same month and year as the first dose date of study drug, the date of first dose of study drug will be used as the onset date of the AE. Otherwise, the first day of the month will be used to complete the onset date of the AE;
 - If the day and month parts of the AE onset date are missing and occur in the same year as the first dose of study drug, the date of the first dose of study drug will be used as the onset date of the AE. Otherwise, January 1st will be used to complete the onset date of the AE;
 - If the AE onset date is completely missing, the date of the first dose of study drug will be used as the onset date of the AE.
- For end date:
 - If only the day part of the AE end date is missing, the last day of the month will be used to complete the end date of the AE;
 - If the day and month parts of the AE end date are missing, December 31st will be used to complete the end date of the AE;
 - If the AE end date is completely missing and the onset date of the AE occurs after the date of the first dose of study drug, the date of last dose plus 30 days will be used as the AE end date. If the AE end date is completely missing and the onset date of the AE occurs prior to the date of the first dose of study drug the date of the first dose of study drug will be used as the AE end date.

Medications:

- For onset date:
 - If only the day part of the medication onset date is missing and occurs in the same month and year as the first dose date of study drug, the date of first dose of study drug will be used as the onset date of the medication. Otherwise, the first day of the month will be used to complete the onset date of the medication;

This document is confidential.

- If the day and month parts of medication onset date are missing and occur in the same year as the first dose of study drug, the date of the first dose of study drug will be used as the onset date of the medication. Otherwise, January 1st will be used to complete the onset date of the medication;
- If the medication onset date is completely missing, the date of the first dose of study drug will be used as the onset date of the medication.
- For end date:
 - If only the day part of the medication end date is missing, the last day of month will be used to complete the end date of the medication;
 - If the day and month parts of medication end date are missing, December 31st will be used to complete the onset date of the medication;
 - If the medication end date is completely missing and the onset date of the medication occurs after the date of the first dose of study drug, the date of last dose plus 30 days will be used as the medication end date. Otherwise, the date of the first dose of study drug will be used as the medication end date.

The partial dates of medical history and prior treatments (BCG, Bladder cancer, systemic anti-therapy and radiotherapy) will not be imputed as they are already defined as prior to the treatment. No further imputation of partial dates to determine the pre/post treatment status is needed.

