## 11. EFFICACY AND SAFETY ASSESSMENTS

### 11.1 Primary Efficacy Variable

The primary efficacy endpoint is, in patients with CIS at baseline, the:

- Proportion that achieves a CR at any time on or after week 12 and within the first 48 weeks

Complete response is defined as at least one of the following:

- Negative cystoscopy and negative (including atypical) urine cytology
- Positive cystoscopy with biopsy-proven benign or low-grade NMIBC and negative cytology
- Negative cystoscopy with malignant urine cytology if cancer is found in the upper tract or prostatic urethra and random bladder biopsies are negative

The complete response in patients with CIS for this endpoint must be documented on or after the Week 12 response assessment and on or prior to the Week 48 assessment. Duration of complete response in patients with CIS will be calculated from the documented onset of the complete response to the assessment where the patient no longer meets the definition of complete response. More generally, recurrence is defined as the reappearance or persistence of high-grade disease, or new high-grade disease. Recurrence must be biopsy proven. Persistence, appearance, or presence of lower grade disease will not be considered recurrence.

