### 13.5.4 Handling of Missing Data

All efforts will be made to avoid missing data. If, however, it does occur, it will be handled as follows:

- If a visit has been missed and cytology results are available at the next visit and no disease is present, then the earlier visit will be counted as absence of disease.
- In addition, the count of absence of disease will be based on visit findings, meaning that if a patient missed a visit and at the next visit he/she experienced a recurrence, the recurrence will be counted only from the day on which evidence was provided.

Patients with CIS lesions that do not resolve by the 12-week cystoscopy will be classified as EFS events. For Kaplan-Meier analyses of EFS, they will be considered to have recurred at 12 weeks.

Any patient without tumor in the bladder but presence of tumor in the upper urinary tract will not be classified as failures in the CR and EFS analyses and will continue study participation.

Additional subgroup analyses may be included in the statistical analysis plan.

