5.1 Efficacy Endpoints

5.1.1 Primary Efficacy Endpoint

The primary efficacy endpoint is, in patients with CIS at baseline, the:

- Proportion that achieves a CR at any time on or after week 12

Complete response is defined as at least one of the following:

- Negative cystoscopy and negative (including atypical) urine cytology
- Positive cystoscopy with biopsy-proven benign or low-grade NMIBC and negative cytology
- Negative cystoscopy with malignant urine cytology if cancer is found in the upper tract or prostatic urethra and random bladder biopsies are negative

The complete response in patients with CIS for this endpoint must be documented on or after the Week 12 response assessment. Duration of complete response in patients with CIS will be calculated from the documented onset of the complete response to the assessment where the patient no longer meets the definition of complete response. More generally, recurrence is defined as the reappearance or persistence of high-grade disease, or new high-grade disease. Recurrence must be biopsy proven. Persistence, appearance, or presence of lower grade disease will not be considered recurrence.

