7.3.1 Primary Efficacy Analysis

The primary endpoint of the study is the CR rate in patients with CIS, supported by duration of the CR.

A CR in patients with CIS is defined as at least one of the following:

- Negative cystoscopy and negative (including atypical) urine cytology
- Positive cystoscopy with biopsy-proven benign or low-grade NMIBC and negative cytology
- Negative cystoscopy with malignant urine cytology if cancer is found in the upper tract or prostatic urethra and random bladder biopsies are negative

The CR in patients with CIS for this endpoint must be documented on or after the Week 12 response assessment. Duration of CR in patients with CIS will be calculated from the documented onset of the CR to the assessment where the patient no longer meets the definition of CR. The durability of the CRs will be described using Kaplan-Meier plots of the duration of CR in responders. A tabular summary will also be created showing the proportion of patients with baseline CIS who are in response at 12, 24, 36, 48, 72 and 96 weeks using Kaplan-Meier estimates incorporating censoring (note that any patient who achieves response within 4 weeks of the planned assessment will be considered to be in response at that assessment, ie, a patient who has CR at 16 weeks will be a responder at 12 weeks). A similar tabular

This document is confidential.

summary will be created in the subset of patients with CIS who achieve a CR, that remain in response 12, 24, 36, 48, 52, 60, 72 and 84 weeks after the onset of response, for this summary, two methods will be used one which incorporates censoring and a second where patients who leave the study without losing response are considered failures. A by-patient swim lane plot of the time to CR and duration of CR in patients with CIS who respond will also be created. A similar summary will be created for the EFS (in all patients).

Sensitivity analyses for duration of response will be performed starting from the time the CIS lesion clears to time that new CIS lesions are identified, censoring patients with no CIS but other high-grade disease at the time of recurrence and a separate analysis looking at the time from response until any NMIBC is found (including low-grade disease).

A listing of CR rate and duration of response will be provided.

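### The missed-visit rule can credit a baseline-CIS patient with a disease-free Week 12 that nobody observed, and the SAP does not say whether it yields to the CR rules in 7.3.1

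*SAP*

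**What the plan says.** SAP 7.1.3 opens its efficacy rules with "For efficacy endpoints, all efforts will be made to avoid missing data", so what follows covers efficacy endpoints generally. If a visit is missed and the next shows no disease, "then the earlier visit will be counted as absence of disease". There is no exception for baseline CIS and no condition on the patient's status before the gap.

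Protocol 13.5.4 has the same rule but describes the evidence differently: "If a visit has been missed and cytology results are available at the next visit and no disease is present". The SAP names both cytology and cystoscopy, with no word joining them.

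Three other provisions bear on the same patient:

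- **Documentation.** SAP 5.1.1 and 7.3.1 say that CR "must be documented on or after the Week 12 response assessment", and duration runs from the documented onset of CR.
- **Timing.** For the response-by-week table, SAP 7.3.1 allows a 4-week margin, with the example that "a patient who has CR at 16 weeks will be a responder at 12 weeks".
- **EFS.** SAP 7.3.2.1 makes failure to clear CIS by the Week 12 cystoscopy an EFS event.

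The only missed-visit sensitivity analysis in SAP 7.3.2.1 concerns a missed visit followed by a recurrence.

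**The concern.** Filling a gap between two clear assessments is reasonable. A patient with baseline CIS who has not yet been assessed is in a different position, because the last known state is disease. The rule then assigns clearance at a visit where nothing was seen, on the strength of a result 12 weeks later.

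EFS at 12 weeks in the CIS subgroup is a named secondary endpoint, and the matching secondary objective is the proportion without high-grade recurrent or persistent disease at that time. The SAP also plans a table of the proportion in response at 12 weeks. Two programmers following this SAP could report different Week 12 results, since one section calls the visit disease-free and another would not count a first CR at Week 24. The evidence standard is also unsettled: the protocol's trigger mentions cytology only, while the CR definition combines cystoscopy and cytology.

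**Working it through.** **1. The plan's own figures.** Inputs from SAP 7.1.5: null rate 20%, exact binomial test, two-sided 0.05.

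- n = 70: the smallest r with P(X ≥ r | 0.20) ≤ 0.025 is 22 (tail 0.0159). Power is P(X ≥ 22 | 0.40) = 94.5%, marginally below the stated figure of over 95%.
- n = 100: r = 29 (tail 0.0200). Power is P(X ≥ 29 | 0.35) = 91.5%, against about 92% stated.
- Interim, n = 35 (SAP 7.5): P(X ≥ 10 | 0.40) = 94.2% and P(X ≤ 9 | 0.15) = 97.1%, as stated.

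None of these depends on the missed-visit rule.

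**2. One patient followed through the outputs.** Baseline CIS, Week 12 missed, documented CR at Week 24.

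| Output | With carry-back | Without | Change |
|---|---|---|---|
| Primary CR | CR | CR | 0 |
| Duration of CR | starts Week 24 (documented onset) | starts Week 24 | 0 |
| Response table, Week 12 | 7.1.3: absence of disease; 7.3.1: not in response (24 − 12 = 12 weeks, more than 4) | not in response | depends on which rule prevails |
| Kaplan-Meier EFS, Week 12 | no event | no event, unless a missed Week 12 is presumed a failure | 0 as written |
| Disease-free proportion, Week 12 | counted disease-free | not observed | up to 1/n |

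The first row is the same under either endpoint window. The SAP has "Proportion that achieves a CR at any time on or after week 12", and the protocol closes the window at the Week 48 assessment; Week 24 lies inside both.

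If a programmer used the imputed visit as onset, duration would lengthen by 12 weeks. For example, with CR lost at Week 60 it would be 60 − 12 = 48 weeks instead of 60 − 24 = 36.

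**3. Size.** Let k be the number of baseline-CIS patients who miss Week 12 and are clear at Week 24. If they are counted as not cleared, the Week 12 proportion falls by k/n. For illustration, take the responder counts at the design alternatives:

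- n = 70, 28/70 = 40.0%: k = 1 gives 27/70 = 38.6%; k = 3 gives 25/70 = 35.7%; k = 5 gives 23/70 = 32.9%; k = 7 gives 21/70 = 30.0%.
- n = 100, 35/100 = 35.0%: k = 1 gives 34.0%; k = 5 gives 30.0%.

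If the patient were instead dropped as not evaluable, k = 1 gives 27/69 = 39.1%, a smaller change. So 1/70 = 1.4 points per patient is a ceiling at n = 70 (1.0 point at n = 100).

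**4. A range for k.** The documents give no missed-visit rate. Assume that 3–10% of CIS patients miss Week 12 and that 30–40% of those are clear at Week 24. Then 0.03 × 0.30 = 0.9% and 0.10 × 0.40 = 4.0%, which is 0.6 to 2.8 of 70 patients.

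**The case against.** The strongest reply is that the specific rule governs the general one. SAP 7.1.3 speaks of absence of disease, not CR. CR has its own definition, must be documented, and has its own 4-week margin. A reader might infer that the plan scores an unobserved Week 12 as a response and adds 12 weeks of duration. The documents do not support that: duration runs from documented onset, and the 4-week margin keeps a first CR at Week 24 out of the Week 12 response table.

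A reader might also infer that Kaplan-Meier EFS is inflated. That would require a missed Week 12 to count as failure to clear, and neither document says so. Recurrence must be biopsy proven, and a patient seen clear at Week 24 has no documented event.

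Nor does every choice lean towards the drug. The SAP re-dates recurrence to the missed assessment in a sensitivity analysis, dates unresolved CIS as recurrence at 1 day, and adds a duration summary that counts patients who leave while in response as failures.

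Missed Week 12 visits may also be rare. The assessment is mandatory for CIS patients, both tests must be evaluated before dosing, and SAP 7.1.2 keeps a late assessment under its recorded visit. On the evidence standard, the protocol rule also requires that no disease be present, and the missing conjunction in the SAP may be typographical.

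All of this limits the effect. It does not supply the missing condition. Section 7.1.3 applies to efficacy endpoints without exception, the SAP states no order of precedence, the protocol names cytology alone, and no planned analysis tests a clear result carried back.

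**Conclusion.** The point holds in a limited form. As written, the rule gives an unobserved disease-free Week 12 to a baseline-CIS patient never yet shown clear on study, and it is not reconciled with the 4-week and documented-CR provisions of SAP 7.3.1. The consequence is an upward bias in the Week 12 disease-free (EFS) proportion among CIS patients, set against counting such patients as not cleared. It is at most 1.4 points per affected patient at n = 70. Under the assumed rates it is about 1 to 4 points; those rates are assumptions, and the true number may be close to zero.

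The primary CR rate, its confidence interval, the power and the interim CR count are unaffected. Duration of CR is unaffected unless the imputed visit is wrongly taken as onset. This should be corrected because a named secondary endpoint is left open to two readings and the correction is simple, not because the main conclusion is at risk.

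**What to change.** 1. In SAP 7.1.3 and protocol 13.5.4, limit the carry-back to patients with an earlier documented disease-free assessment on study.
2. In both places, require negative cystoscopy and negative cytology at the next visit, or findings that otherwise meet the CR definition.
3. State that SAP 7.3.1 prevails for response status and CR onset in baseline-CIS patients, so that a missed Week 12 with no CR within 4 weeks is not counted as in response at Week 12.
4. Add a sensitivity analysis of Week 12 EFS in CIS patients that counts a missed Week 12 as not cleared.

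The cost is a few sentences in each document and one extra table. The Week 12 proportion may come out slightly less favourable. Item 1 as worded also reaches papillary-only patients who miss Week 12. They enter after complete resection, so if the sponsor does not want the limit to apply to them, the text should say so.

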### **13.5.3 Secondary Efficacy Analyses**

The secondary efficacy endpoints include the following:

- The incidence of EFS at 48 weeks, where EFS is defined as high-grade recurrence-free survival (overall population and subgroup of patients with CIS)
- The incidence of EFS at 12, 24, 36, 72, and 96 weeks, where EFS is defined as high-grade recurrence-free survival (overall population and subgroup of patients with CIS)
- Time to recurrence; recurrence is defined as an EFS event
- The incidence of PFS at 48, 72, and 96 weeks as well as time to progression estimated using Kaplan-Meier methods. Progression is defined as the development of T2 or greater disease. Sensitivity analyses will also be performed and will include any of the following as progressions:
  - An increase in stage from Ta or CIS to T1, or
  - Development of T2 or greater, or
  - Lymph node disease, or
  - Distant metastasis
- Overall survival of patients enrolled in the study at 48, 72, and 96 weeks and survival time estimated using Kaplan-Meier methods
- Changes in quality of life over time, as measured by EORTC QLQ-C30 and QLQ-NMIBC24

Additionally, patients with appearance of new high-grade disease (ie, new high-grade papillary disease in patients with CIS only or new CIS in patients with papillary disease only) will be classified as treatment failures, as will patients with CIS at baseline whose CIS lesions have not resolved by the 12-week cystoscopy.

Any patient without tumor in the bladder but presence of tumor in the upper urinary tract will not be classified as failures in these analyses and will continue study participation.

Rates will be summarized using two-sided 95% confidence intervals (using Kaplan-Meier estimates incorporating censoring for PFS and overall survival and both Kaplan-Meier estimates and exact binomial methods for EFS). Time to recurrence and other endpoints will be examined using Kaplan-Meier methods, with plots for the entire patient population, for subgroups of patients with papillary lesions only, and for patients with CIS (with or without papillary lesions). Time 0 is the time of first treatment with BC-819.

Further sensitivity and subgroup analyses will be described in the statistical analysis plan.

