7.3.2.1 Event-Free Survival and Time to Recurrence

EFS is defined as the time from first dose of study medication to the first recurrence of disease or death from any cause. Recurrence of disease is defined as

- Appearance of new high-grade disease (ie, new high-grade papillary disease or new CIS) or
- Failure to clear CIS lesions by Week 12 cystoscopy in patients with CIS at baseline

Recurrence must be biopsy proven. Persistence, appearance, or presence of lower grade disease will not be considered recurrence in the primary EFS analyses. Sensitivity analyses will be performed with lower-grade disease also considered an EFS event.

Any patient without tumor in the bladder but presence of urothelial carcinoma in the upper urinary tract or prostatic urethra will not be classified as failures in these analyses and will continue study participation.

Additionally, the overall proportion of patients who have high grade recurrence (and subcategories of persistent CIS, new CIS, new high-grade papillary disease), development of T2 or greater or metastatic disease, cystectomy and death will be summarized for the FAS, and the subgroups with CIS and papillary only disease.

Kaplan-Meier methods will be used to estimate the EFS (ie, percent surviving without a recurrence) and the 95% confidence interval at 12, 24, 36, 48, 72, and 96 weeks in all patients in the FAS and the subgroup of patients with CIS. The median EFS (ie, median time to recurrence) and its 95% confidence interval will also be estimated. Kaplan-Meier plots for EFS will be created.

A sensitivity analysis will also be performed to analyze EFS using binomial methods where patients are considered as being recurrence-free if they have documented recurrence-free survival by the specified time point. Only evaluable patients will be included in the analysis. Patients will be considered evaluable if they have enough follow-up to determine recurrence status at the time point being summarized or if they have discontinued treatment. Exact 95% confidence intervals for EFS will be calculated.

This document is confidential.

A sensitivity analysis for EFS will be performed where if a patient missed a visit and at the next visit he/she experienced a recurrence, the recurrence will be counted from the day of the missed assessment. An additional sensitivity analysis will be performed where recurrence of any NMIBC, including low-grade disease, is counted as an EFS event.

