7.7 Changes to Methods Planned in the Protocol

There are no changes from the analysis planned in the protocol.

This document is confidential.

8. Tables, Listings, And Figures

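### The SAP dates uncleared CIS at Day 1 in the Kaplan-Meier EFS analysis where the protocol dates it at 12 weeks, and declares no change; the CIS-subgroup median EFS would probably be 1 day

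*SAP*

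**What the plan says.** Both documents give a rule for CIS that has not resolved by the 12-week cystoscopy, under the same heading, Handling of Missing Data. They differ in the date.

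- Protocol 13.5.4: "For Kaplan-Meier analyses of EFS, they will be considered to have recurred at 12 weeks".
- SAP 7.1.3: "For Kaplan-Meier analyses of EFS, they will be considered to have recurred at 1 day".
- SAP 7.7, on departures from the protocol: "There are no changes from the analysis planned in the protocol".

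SAP 7.3.2.1 ties the event to the Week 12 examination: "Failure to clear CIS lesions by Week 12 cystoscopy in patients with CIS at baseline". On the time scale, the same section states: "EFS is defined as the time from first dose of study medication to the first recurrence of disease or death from any cause". Protocol 13.5.3 fixes the origin: "Time 0 is the time of first treatment with BC-819".

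The outputs that use this date are Kaplan-Meier EFS "at 12, 24, 36, 48, 72, and 96 weeks in all patients in the FAS and the subgroup of patients with CIS", and the median: "The median EFS (ie, median time to recurrence) and its 95% confidence interval will also be estimated". SAP 7.3.2.1 repeats every EFS analysis for time to recurrence. SAP 7.6 uses Kaplan-Meier EFS at 48 weeks for the subgroups, and SAP 10.1 lists Kaplan-Meier EFS and time-to-recurrence outputs for the interim analysis.

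**The concern.** A programmer who follows the SAP departs from the protocol, and a reader of SAP 7.7 would not know it. Day 1 also fits poorly with the rest of the SAP. The event is known only at the Week 12 cystoscopy, and the visit tables schedule none between screening and that visit. SAP 7.1.3 itself dates a recurrence found after a missed visit from the day the evidence appears, which is the opposite principle.

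Two outputs are at stake. One is the median EFS, which in the CIS subgroup could be set by the dating rule at the first day of treatment. The other is EFS from Week 12 onward. Patients who leave before they can be assessed may count in the denominator on Day 1, when all the non-clearance events are placed, although nobody knows whether they would have cleared.

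**Working it through.** **The plan's own figures.** The documents give no EFS estimate, so the check uses the CR planning rates in SAP 7.1.5: 40% with 70 CIS patients and 35% with 100, against 20%. An exact binomial test with upper-tail error of at most 0.025 gives:

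- n = 70: reject at 22 or more responses; power 94.5% at 40% (stated as over 95%, so marginally below).
- n = 100: reject at 29 or more; power 91.5% at 35% (stated as about 92%).

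These are close enough to use the rates as inputs.

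**Median, no censoring before Week 12.** Assume that the share clearing CIS at Week 12, p, equals the planning CR rate. The number of non-clearances is d = (1 − p) × n, and the curve after they are counted is 1 − d/n.

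| CIS patients | p | d | Curve after these events | Median, SAP rule | Median, protocol rule |
|---|---|---|---|---|---|
| 70 | 40% | 42 | 40% | 1 day | 84 days |
| 100 | 35% | 65 | 35% | 1 day | 84 days |

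Allowing for binomial variation in d, the chance that at least half of the CIS patients fail, so that the median is 1 day, is 96.5% in the first case and 99.9% in the second.

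In the whole FAS of 140, a 1-day median needs at least 70 Day 1 events. The expected shares are 42/140 = 30% and 65/140 = 46%, both below half. With 100 CIS patients and only 20% clearance the share is 80/140 = 57%, and the overall median would also fall on Day 1.

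**EFS at Week 12, with early censoring.** Let c of N CIS patients leave unassessed before Week 12, and suppose they are censored on or after Day 1.

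- SAP rule: S = 1 − d/N, because the c patients are still at risk when the events are counted.
- Protocol rule: S = 1 − d/(N − c), because they have already left the risk set.

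If leaving is unrelated to outcome and a share q leaves, then c = qN and d = (1 − p)(1 − q)N. The SAP rule gives p + q(1 − p) and the protocol rule gives p. The excess is q(1 − p).

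Example: N = 100, p = 40%, q = 10%. Then c = 10 and d = 0.6 × 90 = 54. The SAP rule gives 1 − 54/100 = 46%; the protocol rule gives 1 − 54/90 = 40%.

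| p | q (assumed) | SAP rule | Protocol rule |
|---|---|---|---|
| 40% | 0% | 40% | 40% |
| 40% | 5% | 43% | 40% |
| 40% | 10% | 46% | 40% |
| 40% | 20% | 52% | 40% |
| 35% | 10% | 41.5% | 35% |

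Simulation of 20,000 trials per scenario agreed with these values where it was run (n = 70 at 40% with 5%, 10% and 20% censored; n = 100 at 35% with 10%). After Week 12 both curves have the same risk sets, so the ratio of the two estimates (46/40 = 1.15 in the example) carries through to Week 96. In the 20% row the SAP curve stays above one half on Day 1, so there the median is no longer 1 day.

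**If the same patients are censored before Day 1.** The risk set on Day 1 is already N − c, both rules give 1 − d/(N − c), and there is no excess.

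**The case against.** Day 1 could be deliberate. The plan counts persistence of high-grade disease as recurrence, and a patient who never cleared CIS was never free of disease. A 12-week median would also be an assigned date, not an observed onset. This is a fair case for choosing Day 1, but not for leaving it undeclared while SAP 7.7 denies any change.

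A reader might infer that the SAP rule necessarily inflates EFS. The documents do not establish that. The SAP states no censoring rule for EFS. Its rule for time to recurrence censors at the last assessment without recurrence. Someone who leaves before Week 12 has only the screening cystoscopy, so read literally the censoring date precedes Day 1 and the inflation disappears. Nor do the documents give an early dropout rate.

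The link between CR and EFS is also approximate. Under SAP 5.1.2, a patient with three or more positive cystoscopy or cytology results but repeatedly negative biopsies is not an EFS failure, so a non-responder need not be an EFS event.

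Fixed 12-week dating has a weakness of its own. The cystoscopy may be done up to 14 days before the visit, so a patient who cleared, was assessed before Day 84 and then left could be censored just before the failures are counted, which lowers EFS. That supports writing the censoring rule out in full; it does not support Day 1.

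Finally, EFS is a secondary endpoint that is estimated without a hypothesis test, and the planned binomial EFS analysis does not use the event date. This limits the severity.

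**Conclusion.** The contradiction is certain: the two current documents give different dates for the same event, and the SAP states that nothing changed. None of the sensitivity analyses listed in SAP 7.3.2.1 re-dates this event.

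At the planning rates, with Week 12 clearance equal to the CR rate and no early censoring, the CIS-subgroup median EFS is 1 day instead of 12 weeks. A reader might extend this to the whole trial population, but the expected Day 1 share there is 30% to 46%, so the overall median is usually not 1 day.

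The upward bias from Week 12 onward is conditional. It needs patients censored on or after Day 1 and before Week 12, and its size is about the share so censored times one minus the clearance rate. The 5%, 10% and 20% shares are assumptions. With no such patients the landmark rates agree.

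The primary CR rate and the futility rule, which counts CRs, are unaffected. This should be fixed, as a defect in secondary endpoints; it does not threaten the main conclusion of the trial.

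**What to change.** In SAP 7.1.3, replace 1 day with the protocol's 12 weeks, for both EFS and time to recurrence. In SAP 7.3.2.1, add the EFS censoring rule, saying how patients with no Week 12 assessment are handled and how an assessment done in the 14 days before the visit is dated.

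If Day 1 is intended, declare and justify it in SAP 7.7 and report the protocol's 12-week rule alongside.

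The date correction costs one sentence and one line of code; the censoring rule adds a short paragraph. No data collection changes.
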